lead) at the therapeutic target. Unilateral ECoG recordings are obtained from the right frontoparietal region by advancing a subdural ECoG strip with eight 4 mm platinum contacts (1 cm inter-contact spacing) posteriorly through the burr hole used for DBS implantation and an additional lead (4 contact) anteriorly towards the prefrontal cortices (Figure 4). Unilateral ECoG is planned to mitigate risk. Intraoperative fluoroscopy is used for anatomical localization as extensively described in our previous work.⁵⁰ We use the Freesurfer cortical parcellation and the Desikan-Killiany atlas⁵³ to identify pre and postcentral gyri and middle frontal gyrus and select the contacts for analysis respectively. DBS leads are localized postoperatively with lead-DBS⁵⁴ (Figure 4) using preoperative structural MRI and postoperative CT scan. For M1, we identify the first ECoG contact anterior to the central sulcus and completely overlying the precentral gyrus. Anterior scalp reference and left retroauricular ground are used, to enable subsequent re-referencing. Neurophysiological signal acquisition, stimulus presentation, and recordings of behavioral responses are controlled via a single computer running BCI2000.⁵⁵ Signals are amplified (AlphaOmega, NeuroOmega) using a sampling rate of 44 kHz (microelectrode recordings) and 1.3 kHz (macroelectrode and ECoGs recordings).

The following timeline will be followed during the above surgical procedure:

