The patient will emerge from anesthesia for clinical placement of the left DBS electrode and neurological testing done by [name] and the neurologist. Once clinical testing is complete, the ECoG strip will be placed on the right side for research purposes. Then, [name] will continue with the clinical procedure and place the right DBS electrode and conduct neurological testing to confirm placement. The researchers will connect ECoG and DBS leads to the Neuro-Omega system to record brain signals throughout research related tasks. Once all clinical testing has been completed, the research team will simultaneously record cortical ECoG and pallidal LFP from GPI/GPe during both induction and emergence with target-controlled infusion of propofol detailed above. During induction and emergence, the participant will also complete the behavioral task detailed above. If data is being collected for **Specific Aim 2**, ECoG /LFP recordings and behavioral assessments will take place with no stimulation. If data is being collected for **Specific Aim 3b**, recordings and behavioral assessments will be made during both induction and emergence of anesthesia with either GPI or GPe stimulation. When the research portion is complete, the ECoG strips will be removed and the surgery will finish per clinical standard of care.

DATA ANALYSIS

LFP Analyses:

Signal analysis is performed in MATLAB (The Mathworks Inc., Natick, MA). Data is parsed into various behavioral and stimulation state epochs, excluding any sections containing electrical or movement artifact using methods previously described.^{41, 50} Bipolar re-referencing of adjacent contacts is used in order to emphasize local and minimize global signals, which is critical for the proposed network coupling analyses across brain regions. 60 Hz line noise is rejected using a notch filter. 60 Hz line noise is rejected using a notch filter.

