Power spectra are obtained by applying non-overlapping windows in time series using Thomson's multi-tapering method⁵⁹ or Welch method and 1 Hz frequency resolution. To minimize stimulus artifact during stimulation trials, we employ the following critical steps: (1) bipolar referencing to minimize common stimulation artifacts in adjacent contacts (2) monopolar deep brain stimulation with current return at the shoulder (analogous to chronic generator implant) (3) bipolar recordings flanking the site of deep brain stimulation in order to minimize differential stimulation artifact between the two recordings leads (4) amplifier grounding on the contralateral hemibody (5) high frequency sampling (to minimize aliasing) (4) signal preprocessing to filter stimulation frequency and (6) employing Hampel filters to eliminate residual stimulus related noise. The Hampel filter uses the outlier robust Hampel identifier to detect peaks in the power spectra attributable to the stimulation frequency and replaces them with the median value of local, adjacent values.⁶⁰ Using this multi-tiered approach to recording and signal processing, we have successfully recorded cortical activity during subcortical stimulation.^{41, 42}

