PK-PD Model Fitting. The pharmacodynamic responses for both behavioral endpoints will be modeled with a sigmoidal E_{max} function: $Fraction_{responsive} = 1 - C_e^{\gamma} / (C_{e50}^{\gamma} + C_e^{\gamma})$; Where Ce is the effect site concentration, Ce₅₀ is the effect site concentration at which half of the population is no longer responsive, and γ is the Hill coefficient governing the slope of the sigmoid. Fitting will be done using NONMEM (ICON Development Solutions) and parameter estimation. Comparison of Ce₅₀ values between PD and ET populations will be made using 95% confidence limits on the resulting parameter fits. Additional exploratory analyses of the model will attempt to account for heterogeneity in the PD population by constructing candidate models that nest the PD effect by both UPDRS scores and covariates of cognitive function (MoCA), utilizing a drop of corrected Akaike Information Criterion (AIC) by 20 points as a threshold for a significant improvement from adding a parameter to the model.

Specific Aim 2:

We will temporally correlate the evolution of behavioral measures of LOC/LOR (including loss of spontaneous movement and loss of movement to command, with digital synchronization with neurophysiological recordings through digital event recording) with I changes in GPi vs GPe pallidocortical circuits. Techniques outlined in LFP analyses above will be implemented to complete assessment.

Specific Aim 3a:

Statistical analysis pipeline outlined in Aim 1 will be replicated in Aim 3a.

Specific Aim 3b:

Recordings and behavioral assessments will be compared to results acquired in Aim 2. Techniques outlined in LFP analyses above will be implemented to complete assessment.

SAMPLE SIZE

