		 CMC	 Yes
		 THR	 Yes
		 TSRH	 Yes
		 Other: UCLA	 Yes
2	GPI/GPe high frequency stimulation	 UTSW	 Yes
		 PHHS	 Yes
		 CMC	 Yes
		 THR	 Yes
		 TSRH	 Yes
		 Other: UCLA	 Yes

4.c. Risk:Benefit Analysis of study interventions being tested or evaluated under this protocol

For each study intervention identified in section 6b above, complete a risk:benefit analysis table.

(Two tables are provided, copy & paste additional tables as needed or delete both tables if this study does not test an intervention)

Form A

IRB #	STU 2021-0396
-------	---------------

**4.c.
Study Intervention #1
Propofol Administration**

List each group exposed to this intervention on a separate line.
(e.g., experimental, control, Arm A, Arm B, etc)
Or state All Groups/Subjects

For each group, list the **benefits** of this intervention. (Benefits can be directly from the intervention or from a monitoring procedure likely to contribute to the subject's well being). If there are no benefits, state "none".

All groups

No benefit

If you are requesting a Waiver of Informed Consent, complete the table below.

If you have a consent form, **list the reasonably foreseeable risks in the consent form (and do not complete this section).**

List the risks according to the probability (likely, less likely or rare) and magnitude (serious or not serious).
(include: 1) expected adverse events; 2) rare and serious adverse events; 3) all other psychological, social, legal harms)
Do not delete frequency. Frequency must be estimated because it will assist you with determining which adverse events will require prompt reporting.

	Not serious	Serious
Likely These risks are expected to occur in more than 20 out of 100 subjects.	•	•
Less likely These risks are expected to occur in 5-20 subjects or less out of 100 subjects.	•	•
Rare These risks are expected to occur in less than 5 subjects out of 100		•

Form A

IRB #	STU 2021-0396

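### Nothing commits the plan to processing unstimulated Aim 2 recordings like Aim 3b recordings, so the pallidal contrast can mix montage and filtering with the DBS effect

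*Combined protocol and SAP*

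**What the plan says.** Section 4.a, Data Analysis, LFP Analyses sets the general montage: "Bipolar re-referencing of adjacent contacts is used in order to emphasize local and minimize global signals". No aim is excepted. A later paragraph of that section begins "To minimize stimulus artifact during stimulation trials, we employ the following critical steps" and lists seven items. Three of them matter here:

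- "bipolar recordings flanking the site of deep brain stimulation in order to minimize differential stimulation artifact between the two recordings leads"
- "signal preprocessing to filter stimulation frequency"
- Hampel filters, which "detect peaks in the power spectra attributable to the stimulation frequency" and put a local median in their place.

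The stimulation frequency is not given in Hz; table 4.b says only "GPI/GPe high frequency stimulation". Filter type and bandwidth, and the Hampel window and threshold, are not stated.

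For Specific Aim 3b the Data Analysis text says "Recordings and behavioral assessments will be compared to results acquired in Aim 2". Aim 2 is recorded without stimulation (Section 3, and Section 4.a under Specific Aims 2 & 3b). Section 1 makes the comparison of brain signals with and without DBS the primary outcome of Aim 3b. The text refers both aims to the LFP methods in the same words. It describes no matched-montage rule, no sham filtering and no sensitivity analysis for processing.

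**The concern.** A bipolar signal depends on which two contacts are subtracted. A pair that straddles the stimulated contact is wider than an adjacent pair and covers different tissue. If stimulated patients are analysed on one kind of pair and unstimulated patients on the other, a group difference in pallidal power or pallidocortical coupling can arise from the montage alone. Filtering one group around the stimulation frequency can do the same for measures that use high-frequency amplitude. The primary contrast of Aim 3b could then be credited to DBS when part of it comes from processing.

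**Working it through.** **1. The plan's own figure.** Sample Size, Aim 3b gives a one-sample t-test, d = 0.75, power 0.8 (printed as p), alpha 0.05 and 20% dropout. Exact noncentral-t power, two-sided, n = 16, noncentrality 0.75 × √16 = 3.0, is 0.8006; 16 / (1 − 0.20) = 20. Both stated numbers reproduce. (Sidedness is not stated; one-sided would give 13.)

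**2. Which listed steps can differ between the aims.**

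| Listed step | Position for Aim 2 |
|---|---|
| Bipolar referencing | Shared: it is the default |
| Ground on the opposite side | Shared: "Anterior scalp reference and left retroauricular ground are used", with right-sided recording |
| High sampling rate | Shared: 1.3 kHz for all macroelectrode and ECoG recordings |
| Monopolar stimulation | Not applicable: it concerns delivery |
| Flanking pair | No counterpart without a stimulated contact |
| Stimulation-frequency filter | Not stated either way |
| Hampel step | Not stated either way |

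**3. Montage and raw power.** Assume evenly spaced contacts in a row (lead geometry is not given), equal variance s² at each, and correlation rho^k at k spacings. The variance of a contact difference is 2s²(1 − rho^k). The power ratio of two spacings to one is (1 − rho²)/(1 − rho) = 1 + rho.

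| rho (assumed) | Ratio | dB |
|---|---|---|
| 0.5 | 1.50 | 1.76 |
| 0.7 | 1.70 | 2.30 |
| 0.9 | 1.90 | 2.79 |
| 0.95 | 1.95 | 2.90 |

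Uncorrelated contacts give 0 dB. A perfectly uniform gradient doubles amplitude: 20·log10(2) = 6.0 dB.

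**4. Which measures are exposed.** A constant gain g adds 10·log10(g) to absolute power. In a within-patient change it cancels, 10·log10(gP_anes) − 10·log10(gP_rest) = 10·log10(P_anes/P_rest), provided pair and stimulation are the same in both states. Coherence, phase synchrony, phase lag index and the modulation index do not respond to a constant gain either. They are exposed because a wider pair samples different tissue, which step 3 does not size. ECoG strips keep adjacent pairs, so the flanking montage does not reach cortex-only measures.

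**5. Filters.** With a notch at an assumed 100 to 180 Hz, Q 10 to 35, the change at 8 to 30 Hz is at most 0.005 dB. At 90 Hz it reaches 0.9 dB when the notch is at 100 Hz and Q is 10. A Hampel filter confined to the stimulation frequency should leave alpha/beta unchanged. If it ran over the whole spectrum (assumed 11-bin window, 3 MAD), simulated 13 to 30 Hz power fell about 0.75 dB for a very narrow beta peak (SD 0.8 Hz) and 0.01 to 0.2 dB for wider ones.

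**6. Effect on a test.** The plan uses t-tests between conditions. With 16 v 16 patients, no DBS effect and a pure processing shift (assumed, in SD units), the noncentrality is shift/√(1/16 + 1/16) on 30 df.

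| Shift (SD) | Rejection rate at nominal 5% |
|---|---|
| 0 | 5.0% |
| 0.10 | 5.9% |
| 0.25 | 10.5% |
| 0.50 | 27.8% |

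The documents give no between-patient SD of pallidal power, so the decibels in step 3 cannot be converted into these shifts.

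**The case against.** The strongest reply is that both aims are assigned the same LFP methods in identical words, and that three items on the stimulation list are demonstrably shared with Aim 2. A reader might infer that the flanking pair and both filters are withheld from Aim 2. The documents do not say so, and being on the list does not prove it. Section 4.a also points to the grant and to previously described methods, where matched processing might be set out. For the two filters this stands: the text is silent. For the flanking pair it does not. That pair is defined by a stimulated contact, Aim 2 has none, and without a rule assigning a notional site the shared wording cannot be carried out.

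A reader might also infer that a GPi-versus-GPe comparison of neural signals is confounded with recording location. Section 3 states that cohort comparison for Aim 3a, whose described data are behavioural and PK-PD. For Aim 3b it states only a comparison with Aim 2. The problem arises only if such a neural contrast is added.

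Finally, an identical filter chain need not act identically. With no stimulation peak present, a Hampel step does nothing or removes real peaks. This stands, and the fix allows for it.

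**Conclusion.** The point holds in a limited form. Followed as written, the plan takes pallidal measures from different montages in Aim 3b and Aim 2, and leaves open whether they are filtered alike. Absolute pallidal power and coupling that involves the pallidal node are exposed to the montage difference. High-frequency measures such as PAC amplitude are exposed to any filtering difference. The alpha/beta band, on which the power analysis rests, is barely touched by a filter confined to the stimulation frequency.

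The 1.8 to 2.9 dB figure rests on assumed correlations and even contact spacing. A reader might infer a bias of up to 6 dB in every band. That would need a perfectly uniform gradient and applies to raw power on a pallidal pair, not to coupling measures, cortical channels or within-patient dB change. A spurious difference can appear; with the lower bound at 0 dB, nothing shows that it must. The change is still worth making, because the exposed measures are central to the Aim 3b primary outcome.

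**What to change.** Add one paragraph to LFP Analyses covering every Aim 3b versus Aim 2 comparison that involves the pallidal lead:

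- Re-montage the stored Aim 2 recordings to the contact pairs used under stimulation, one set matched to GPi and one to GPe, and compare each stimulated group with its matched set.
- Apply the same stimulation-frequency filter to both groups.
- Apply Hampel replacement in both groups, or exclude the same stimulation-frequency bins in both. Exclusion avoids the unequal action noted above.
- State the filter and Hampel settings.
- If a GPi-versus-GPe neural contrast is made, express it as the difference from the matched Aim 2 montage, or use the common cortical channels.

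The cost is offline reprocessing. Section 4.a records from all four or eight lead contacts, uses a scalp reference chosen to allow later re-referencing, and localizes leads after surgery, so the material should be available. The targets of 16 evaluable and at least 20 recruited do not change. The small downside is that Aim 2 data lose the same filtered bins in this comparison.

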For all specific aims:

Prior to conducting any research related tests / procedures, the patient will be consented. The consent process will be facilitated by the IRB approved research coordinator and will occur in a private room in the pre-operative area prior to surgery. Once in the operating suite, the patient will be put under anesthesia for clinical purposes for surgery. Privacy will be maintained by limiting the individuals in the operating room to only necessary IRB approved research personnel. In addition, all data collected during the study will be immediately de-identified and stored on an encrypted, password protected server.

Behavioral Assessments. For each experiment, three behavioral responses will be evaluated: (1) loss/recovery of spontaneous movement (i.e., loss and recovery of responsiveness (LOR/ROR)) (2) loss/recovery of movement in response to stimuli (separately to clicks [non-salient] and verbal stimuli [salient], as per prior work by Purdon and colleagues⁴), and (3) loss/recovery of movement to command (verbal command with patient name with instruction to show different numbers of fingers, as proxy of loss/recovery of consciousness (LOC/ROC)). Stimuli will be presented in an interleaved fashion every 4 seconds binaurally via headphones (15 presentations of each stimuli at each dose, total 5 min per dose, or until failure to respond 3 times in a row to a certain stimulus). We use these separate measures because of the literature and our hypothesis that circuits mediating responsiveness and consciousness are separable. Namely, numerous studies highlight that consciousness (defined as ability to interact with the environment, most often measured by the isolated forearm test) can be maintained even with loss of responsiveness.^{39, 56}

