Measures of Network Coupling (bivariate, assessed over time and trials) In our approach, when we refer to analyzing "network coupling," we will investigate a broad range of coupling measures. The measures and their rationale are summarized here. Coherence, the most commonly used measure of LFP coupling, is used to describe the degree of co-variability between signal pairs over different frequency ranges.⁶¹ To find the time-frequency representation of coherence for pairs of signals, we use a moving window approach and multi-taper method. Phase synchrony index, a measure of consistency of phase differences between two signals, is used to separately evaluate the specific role of phase difference on neurophysiological observations. Phase locking is of particular interest as fixed phase relationships may be particularly detrimental to information transfer across nodes.⁶² Phase-Amplitude Coupling (PAC) is assessed both locally and across nodes and across time and across trials and is quantified using modulation index (MI).⁶³ PAC is a critical measure that has been identified as a putative pathophysiological mechanism and our group has previously shown to be a potential mechanism for long distance coordination of physiological signals.¹⁶ MI is a method based on Kullback-Liebler (KL) divergence used to extract PAC, described previously. In order to extract the phase from phase signals corresponding to the peak of amplitude signal which we refer to as preferred phase, the weights of the phaseamplitude histogram were used as amplitudes of a vector, while the center phase of each bin constituted the phase of the vector. Statistical significance of MI values is evaluated using surrogate data analysis (by circularly shifting one series relative to the other). MI values are then converted into z-scores and false discovery rate (FDR) is used to correct p-values for multiple comparisons.⁶⁴ Phase lag index (PLI) is used to determine if one signal consistently leads or lags another signal, using non-zero iCoh which indicates an interaction between signals that cannot be due to volume conduction. PLI measures the

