extent to which a distribution of phase angle differences is distributed toward the positive or negative side of the imaginary axis on the complex plane. Specifically, we employ unbiased weighted PLI⁶² in which angle differences are weighted according to their distance from the real axis. We emulate the moving window approach used in the spectral analyses described above, allowing evaluation of patterns of changes in these measures over time. Phase slope index is also used as a measure of the consistency of directional flow within a frequency by determining if the slope of the phase lag between two processes is positive or negative over several adjacent frequency bins, suggesting the direction of signal flow. To assess directionality of the changes, we will perform multivariate granger causality analysis⁶⁵ Similar to the power, connectivity analysis will be performed both across the time^{16, 41-43, 50, 66} and the trials⁶⁷ and with frequency and time resolution similar to the spectral analysis.

Graph theory is used to characterize global network architecture and the inter-relatedness of the nodes.⁶⁸ We will employ weighted connectivity measures to construct functional network diagrams and extract metrics using the Brain Connectivity Toolbox.⁶⁹ Given only 5 nodes, we will compare the following measures across conditions: node degree, clustering, pathlengths, and identification of hubs. Dynamic Causal Modeling (DCM), implemented in SPM70, is used to evaluate causal network architecture rather than separately evaluating pairs of nodes. DCM identifies the most likely among a set of competing models that best accounts for observed neural dynamics, allowing modeling of missing nodes which is critical since human studies preclude evaluation of every node.

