Statistical Analysis is done using SPSS. We assess the significance of connectivity measures by shuffling data to create a permutation distribution and calculating Monte-Carlo estimates of the significance probabilities and/or critical values using parametric/nonparametric statistical tests. We will explore the correlation between behavioral and LFP metrics, and clinical scores (total and lateralized UPDRS-III) using a multiple linear regression model. To confirm generalization to new data points, a "leave one-out" procedure will be employed and finally a coefficient of determination (R²) and RMS of errors will be calculated for all generalization data. T-tests will be used to compare between conditions. To investigate interactions, two factor ANOVA will be used. Gaussian "v-test" and Rayleigh tests will be used to compare the preferred phase angle of connectivity with the uniform distribution to infer phase specificity.⁷¹ The Watson-Williams two-sample test (i.e. circular analogue of the two-sample t-test) will be used to assess whether the mean directions of two groups are identical.

Specific Aim 1:

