Behavioral data analysis and constructing propofol dose response curve. Behavioral data will be collected from both PD and ET patients undergoing generator replacement surgery. Propofol will be administered using a recently published, unified PK-PD for propofol developed to predict the BIS (bispectral index) response to propofol for a broad, diverse population by Eleveld and colleagues, which includes age adjustment, allometric scaling, and parameters for arterial and venous sampling.⁵⁷ (Although not a focus of our work and its value questionable given our underlying hypothesis of altered mesocircuit function in PD, we will record BIS in all patients as an additional data point.) From a range of studies, we expect that in a healthy population loss of responsiveness in 50% of healthy patients will occur with an age-adjusted effect site concentration (Ce₅₀) between 2.71–3.44 µg/ml.⁷⁴ The only published pharmacodynamic studies in PD patients reported a Ce₅₀ of 2.05 and 2.28 µg/ml.^{47, 48} We therefore expect that the dose-response curve for PD patients will be shifted to the left compared to ET patients, who lack basal ganglia pathology. To test this hypothesis, propofol infusion will be initiated with an effect-site concentration (Ce) target of 1.4 µg/ml for 5 min, incremented by 0.3 µg/ml steps every 5 min until loss of behavioral responses (as defined in 3.1.4). One additional incremental step will be performed after loss of responses. Venous serum samples will be drawn at the end of each 5 min step before the next increment. After conclusion of the procedure, target Ce would decrement by 0.3 µg/ml every 5 min until recovery of behavioral responses. Serum sampling will be used to confirm that the Eleveld unified TCI model is functioning as predicted.

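### Across-trial coherence and phase synchrony are compared between behavioral states without equalising trial counts, which can produce a spurious rise in coupling after loss of response

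*Combined protocol and SAP*

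**What the plan says.** Section 4.a, Behavioral Assessments, sets the stimulus schedule: "Stimuli will be presented in an interleaved fashion every 4 seconds binaurally via headphones", with "15 presentations of each stimuli at each dose, total 5 min per dose, or until failure to respond 3 times in a row" to a given stimulus. The number of presentations therefore depends on whether the patient is still responding.

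In the Data Analysis part of the same section, recordings are split into epochs by behavioral and stimulation state. No rule is given for the number of trials or the length of an epoch. The coupling paragraph is headed "Measures of Network Coupling (bivariate, assessed over time and trials". It includes moving-window multitaper coherence and the "Phase synchrony index, a measure of consistency of phase differences between two signals". For the phase lag index alone, the text says "we employ unbiased weighted PLI". The modulation index for phase-amplitude coupling is converted to z-scores against surrogates. Graph metrics are then built from weighted connectivity measures and compared across conditions.

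The Statistical Analysis paragraph says that significance of connectivity measures comes from shuffling data into a permutation distribution, without saying what is shuffled. It then states: "T-tests will be used to compare between conditions".

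**The concern.** Magnitude-based coupling estimates cannot fall below zero, so with a finite number of trials they are positive even when the true coupling is zero, and more so the fewer the trials. A t-test on such estimates tests whether their expected values are equal. That is the same as equal coupling only when the trial counts are equal.

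Here the count is tied to the state under study: full while the patient responds, cut short once responses fail. The bias therefore runs one way, toward apparently higher coupling after loss of response. Neurophysiological data are the primary outcome of Aim 2, and the plan singles out fixed phase relationships as being of particular interest, so the artifact would look like a plausible mechanism. Graph metrics built from the same estimates would carry the bias forward.

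**Working it through.** **The plan's own figure.** Sample Size, Aim 2, gives 16 evaluable patients for a one-sample t-test with d = 0.75, power 0.8 and alpha 0.05. The noncentral t distribution, two-sided, gives power 0.801 at n = 16, and 16/(1 - 0.20) = 20 recruited. Both figures reproduce. They rest on alpha/beta power, not on coupling. The plan gives no figure for coupling bias.

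**Inputs from the documents.** 16 patients; alpha 0.05; 15 presentations per stimulus per dose; stop after 3 consecutive failures, so as few as 3.

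**Assumed, because the documents do not say.** One trial is one stimulus presentation; the t-test is paired within patient and two-sided; 1, 3 or 5 tapers; true coherence 0, 0.1, 0.3 or 0.6, identical in both states; intermediate counts of 11 and 8.

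**Size of the bias with no true coupling.** For n independent estimates:
- Phase synchrony is the length of the mean phase-difference vector, with expected value about √(π/(4n)). For n = 15 this is 0.23. For n = 3 it is 0.51; simulation gives 0.52, the formula being approximate at so small an n.
- Magnitude-squared coherence has expected value 1/n: 1/15 = 0.067 and 1/3 = 0.333.
- With K tapers, n becomes nK, so 3 tapers turn 15 v 3 into 45 v 9.

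**False-positive rate of the t-test.** Complex Gaussian signal pairs, 2,000 simulated studies per cell for most cells. At 15 v 3 trials, phase synchrony and coherence together:

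| True coherence | 1 taper | 3 tapers | 5 tapers |
|---|---|---|---|
| 0 | 99-100% | 97-98% | 97-98% |
| 0.1 | 88-91% | about 42% | 24-25% |
| 0.3 | 53% | 15-16% | 9-10% |
| 0.6 | 21-23% | 8-9% | 7-8% |

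Other counts:
- 15 v 15: about 5%, as it should be.
- 15 v 11, no coupling: 11-14%.
- 15 v 8: about 32-42% with no coupling, roughly 5-15% at true coherence 0.1 or more.
- Pooled steps, 45 v 18, one taper: about 61% with no coupling, 11% or less at true coherence 0.1 or more.

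**Remedies at 15 v 3.**
- Repeated subsampling of the larger state to 3 trials: 4-6%.
- Permuting state labels within patient with counts kept: 4-7%.
- Pairwise phase consistency, (n·PS² - 1)/(n - 1), where PS is the phase synchrony: 5-9% across taper settings.
- Z-scoring each state's phase synchrony against its own surrogates: 6%, 35%, 98% and 100% as true coherence goes from 0 to 0.6. This is not a remedy, because the z-score for a fixed coupling grows with the number of trials.

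**The case against.** The strongest reply is that the plan does not fix the conditions under which the error is large.

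- **What a trial is.** The connectivity text does not define it. The stop rule ends presentations, not recording, and coupling is also to be computed over time in moving windows, where the presentation count need not matter. This stands. But stimulus presentations are the repeated events of the task, and the plan names no alternative and no matching rule.
- **15 v 3 is the extreme.** It describes one stimulus at one step. The step at which response is lost can supply more than 3 presentations, and several unresponsive steps could be pooled: recordings cover induction and emergence, and the Aim 1 text adds that "One additional incremental step will be performed after loss of responses". This also stands. Responsive steps could be pooled too, so the real ratio is unknown.
- **The permutation step.** If state labels are shuffled with counts kept, error stays near 5%. If one signal is shuffled against the other, the test asks whether coupling exists, not whether it differs by state. The one shuffle that the plan does define, for the modulation index, is of the second kind. The t-test sentence stands separately.

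A reader might go further and infer that the t-test will report a false change, that the modulation index is distorted in the same way, or that the Aim 3b comparison fails too. The documents do not support these readings. The error rate depends on coupling strength and taper number, which are not given. The modulation index is z-scored in the plan and was not simulated. In Aim 3b, the same state with and without stimulation falls under the same stop rule, so a difference in counts is conjecture.

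**Conclusion.** The concern holds in a limited form. As written, the plan lets trial count vary with behavioral state and then compares across-trial coherence and phase synchrony by t-test, with neither count matching nor bias correction. If a trial is a stimulus presentation, Aim 2 can show a spurious rise in these two measures after loss of response. With 16 patients and a paired test, the false-positive rate at the extreme imbalance of 15 v 3 lies between about 7-10% and about 99%; it falls with stronger true coupling, more tapers and milder imbalance.

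It does not follow that Aim 2's main result is invalid. The plan states no predicted rise in coupling for that aim, and its sample size rests on alpha/beta power. Moving-window estimates over time, the weighted phase lag index, alpha/beta power, the modulation index and the Aim 3b comparison are not shown to be affected. This should be fixed, but it is not a fatal defect.

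**What to change.** In Measures of Network Coupling and the Statistical Analysis paragraph, define a trial for the connectivity analysis and state what the permutation step shuffles. Then state that across-trial coherence and phase synchrony are compared between states in one of three ways:

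1. after matching trial counts and epoch length within each patient, by repeated random subsampling to the smaller count;
2. with count-unbiased estimators, namely pairwise phase consistency for phase synchrony and bias-corrected coherence;
3. by a within-patient permutation of state labels that keeps the counts.

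Apply the same rule before building graph metrics from these measures. Do not rely on surrogate z-scores for the comparison between states.

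The cost is a few sentences and a small amount of analysis code, with no change to any procedure. Subsampling loses some precision because responsive-state trials are discarded.
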